3. STUDY OBJECTIVES

3.1. PRIMARY

- To assess the antitumor activity of PM01183 in terms of ORR, according to RECIST v1.1, in each cohort of MBC patients.

3.2. SECONDARY

- To further characterize the antitumor activity of PM01183 in terms of duration of response (DR), clinical benefit [ORR or stable disease lasting over three months (SD > 3 months)], PFS, and one-year overall survival (1y-OS).
- To evaluate whether the presence of a known germline mutation in BRCA 1/2 predicts response to PM01183 in MBC patients.
- To explore the activity of PM01183 in specific breast cancer subpopulations according to hormonal receptor status, HER-2 overexpression, number and/or type of prior therapies, or according to other available histological/molecular classifications/parameters.
- To evaluate the safety profile of this PM01183 administration schedule (Day 1, q3wk) in this patient population.
- To analyze the pharmacokinetics (PK) of PM01183 in this patient population.
- To explore PK/PD (pharmacokinetic / pharmacodynamic) correlations, if applicable.
- To evaluate the pharmacogenomic (PGx) expression profile of selected putative markers potentially predictive of response to PM01183, in tissues from tumor samples.

4. SELECTION OF PATIENTS

4.1. INCLUSION CRITERIA

In order to be included into the trial, patients have to fulfill **all** of the following criteria:

All patients

1. Women \geq 18 and \leq 75 years of age.
2. Voluntary signed informed consent form (ICF), obtained from the patient before the beginning of any specific study procedure.
3. Histologically proven diagnosis of metastatic breast carcinoma.
4. No more than three prior chemotherapy-containing regimens for MBC.
5. Patients with known HER-2 overexpressing tumors must have failed at least one prior trastuzumab-containing regimen for metastatic disease.
6. Measurable disease as defined by RECIST v1.1.
7. Eastern Cooperative Oncology Group (ECOG) performance status (PS) 0 or 1.
8. Adequate major organ function:
 - a. Hemoglobin \geq 9 g/dl, prior red blood cell (RBC) transfusions are allowed if clinically indicated; absolute neutrophil count (ANC) \geq 1.5 \times 10⁹/l; and platelet count \geq 100 \times 10⁹/l.
 - b. Alanine aminotransferase (ALT), and aspartate aminotransferase (AST) \leq 3.0 \times upper limit of normal (ULN).

- c. Total bilirubin \leq 1.5 x ULN or direct bilirubin \leq ULN.
- d. Albumin \geq 3 g/dl.
- e. Serum creatinine \leq 1.5 x ULN.
- f. Creatine phosphokinase (CPK) \leq 2.5 x ULN.

9. Washout periods prior to Day 1 of Cycle 1:

- a. At least three weeks since the last chemotherapy (six weeks if therapy contained nitrosureas or systemic mitomycin C).
- b. At least four weeks since the last monoclonal antibody (MAb) containing therapy or radiotherapy (RT) $>$ 30 Gy.
- c. At least one week since the last hormonal therapy.
- d. At least two weeks since the last biological/investigational therapy (excluding MAbs) or palliative RT (\leq 10 fractions or \leq 30 Gy total dose).

10. Grade \leq 1 toxicity due to any previous cancer therapy according to the National Cancer Institute Common Terminology Criteria for Adverse Events (NCI-CTCAE, v4). Grade \leq 2 is allowed in case of alopecia, skin toxicity, asthenia and/or peripheral sensory neuropathy.

11. Patients of child-bearing potential must agree to use a medically approved method of contraception method until at least six weeks after the last study drug administration.

Patients in Cohorts A and A1

12. Known deleterious germline mutation of BRCA1/2.

Patients in Cohort A

13. Prior treatment with PARP inhibitors.

4.2. EXCLUSION CRITERIA

Patients fulfilling **any** of the following criteria will not be included into the trial:

All patients

- 1. Prior treatment with PM01183 or trabectedin.
- 2. Prior RT in more than 35% of the bone marrow.
- 3. Prior or concurrent malignant disease unless in complete remission for more than five years. Exceptions are contralateral ductal or lobular breast carcinoma, adequately treated *in situ* carcinoma of the cervix, basal or squamous skin cell carcinoma, *in situ* melanoma, and *in situ* transitional bladder cell carcinoma, which are allowed to enter the study.
- 4. Histology other than ductal or lobular carcinoma of the breast.
- 5. Symptomatic, steroid requiring or progressive central nervous system (CNS) involvement. In case of known brain metastasis, clinical stability and lack of radiological progression of lesions should be demonstrated for at least the immediate six weeks before study entry.
- 6. Exclusively bone-limited disease.
- 7. Relevant diseases or clinical situations which may increase patient's risk of serious adverse events (AEs) (any of the following):

- a. History of cardiac disease: myocardial infarction or symptomatic/uncontrolled angina within the year prior to enrollment; or congestive heart failure defined as abnormal left ventricular ejection fraction (LVEF) $\leq 50\%$ assessed by multiple-gated acquisition scan (MUGA) or equivalent by ultrasound (US); or symptomatic or treatment-requiring arrhythmia.
- b. Grade ≥ 3 dyspnea or daily intermittent oxygen requirement.
- c. Active uncontrolled infection.
- d. Unhealed wound or presence of any external drainage.
- e. Chronically active hepatitis B virus (HBV) or hepatitis C virus (HCV).
- f. Immunocompromised patients, including those known to be infected by human immunodeficiency virus (HIV).
- g. Known myopathy or persistent CPK elevations $> 2.5 \times$ ULN in two different determinations performed one week apart.
- 8. Pregnant or breastfeeding women.
- 9. Impending need for RT (uncontrolled painful bone metastasis and/or risk of spinal cord compression).
- 10. Limitation of the patient's ability to comply with the treatment or to follow-up the protocol.

Patients in Cohort B

- 11. Known deleterious germline mutation of BRCA1/2.

5. TREATMENT

5.1. STUDY MEDICATIONS

5.1.1. Study Drug Formulation and Supply

PM01183 drug product (DP) is presented as a lyophilized powder for concentrate for solution for infusion with two strengths: 1 mg/vial and 4 mg/vial, which will be supplied by the Sponsors for the purposes of this study.

Before use, the 1-mg vial and 4-mg vial should be reconstituted with 2 ml and 8 ml of water for injection, respectively, to give a solution containing 0.5 mg/ml of PM01183. For administration to patients as an i.v. infusion, reconstituted vials should be diluted either with glucose 50 mg/ml (5%) solution for infusion or sodium chloride 9 mg/ml (0.9%) solution for infusion.

The full composition of the PM01183 1-mg and 4-mg vials and the reconstituted solution per ml is summarized in [Table 1](#).

Table 1. Composition of vials.

Component	PM01183 1 mg	PM01183 4 mg	Concentration per vial after reconstitution
PM01183	1.00 mg	4.00 mg	0.50 mg/ml
Sucrose	200.00 mg	800.00 mg	100.00 mg/ml
Lactic acid	5.52 mg	22.08 mg	2.76 mg/ml
Sodium hydroxide	1.28 mg	5.12 mg	0.64 mg/ml

For instructions regarding drug inventory, handling, reconstitution, dilution, storage and disposal, please refer to the Preparation Guide for PM01183 and the PM01183 IB, both provided as separate documents.

5.2. ADMINISTRATION OF STUDY MEDICATIONS

5.2.1. Route of administration, starting dose, and schedule

Patients included under protocol versions 1.0 and 2.0 will receive PM01183 i.v. as a one-hour infusion on Day 1 q3wk at a starting dose of 7.0 mg FD (three weeks = one treatment cycle).

Patients included from protocol version 3.0 onward (after implementation of amendment no. 2) will receive PM01183 i.v. as a one-hour infusion on Day 1 q3wk at a starting dose of 3.5 mg/m² (three weeks = one treatment cycle). Dose will be capped at BSA of 2.0 m² (i.e., dose will not exceed 7 mg). BSA will be calculated according to standard practice at each center.

PM01183 will be administered over a minimum total volume of 100 ml of solution for infusion (either on 5% glucose or 0.9% sodium chloride) through a central catheter or over a minimum total volume of 250 ml if through a peripheral line, always over one hour at a fixed infusion rate.

5.2.2. Criteria for Treatment Continuation

Before the administration of each dose (re-treatment) on Day 1 of each cycle, patients must fulfill all of the criteria defined in [Table 2](#).

Table 2. Criteria for continuation of treatment.

Variable	Re-treatment
	Day 1
ECOG-PS	≤ 2
Hemoglobin*	≥ 8 g/dl
ANC	≥ 1.5 x 10 ⁹ /l
Platelets	≥ 75 x 10 ⁹ /l
AST/ALT	≤ 3.0 x ULN
Total bilirubin or direct bilirubin	≤ 1.5 x ULN or x ULN
Albumin	≥ 2.7 g/dl
Serum creatinine	≤ 2.0 x ULN
CPK	Grade ≤ 1
Other non-hematological drug-related AEs (except isolated increased GGT and/or AP [‡] , grade 3 asthenia lasting < 1 week, non-optimally treated nausea and/or vomiting)	Grade ≤ 2

* Patients may receive packed red blood cells (PRBC) transfusion and/or erythropoietin (EPO) treatment, if clinically indicated, to increase/maintain adequate hemoglobin levels.

[‡] Any grade accepted for non-drug-related increase of GGT and/or AP.

AE(s), adverse event(s); ANC, absolute neutrophil count; AP, alkaline phosphatase; AST/ALT, aspartate aminotransferase/alanine aminotransferase; CrCl, creatinine clearance; CPK, creatinine phosphokinase; ECOG, Eastern Cooperative Oncology Group; GGT, gamma-glutamyltransferase; PS, performance status; ULN, upper limit of normal.

If a patient does not meet the requirements for re-treatment on Day 1 of any following cycle, regardless of the reason, re-assessments will be performed every 48-72 hours. Treatment will be then withheld, up to a maximum of three weeks beyond its due date, until appropriate recovery.

Patients not meeting re-treatment criteria after a maximum three-week delay the patient must be withdrawn from the trial, except in case of objective clinical benefit (upon Sponsors' agreement).

For any delay lasting more than one week due to treatment-related toxicity (unless exclusively due to neutropenia), a dose reduction must be implemented upon recovery following the rules explained in the next section. Conversely, if the delay was exclusively due to neutropenia related to PM01183, treatment may continue without dose reduction but with appropriate secondary prophylaxis with granulocyte colony-stimulating factor (G-CSF).

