6.2.1. End of Treatment and Off-study

6.2.1.1. End of Treatment

Treatment discontinuation occurs when an enrolled patient ceases to receive the study medication, regardless of the circumstances. By convention, the date of end of treatment will be 30 days after the date of last administration of study drug, unless the patient starts a new antitumor therapy or dies within those 30 days, in which case the date of administration of this new therapy or the date of death will be considered the date of end of treatment.

The primary reason for any discontinuation will be recorded on the patient's Case Report Form (CRF).

If a patient discontinues treatment, every effort should be made to complete the scheduled assessments.

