6.7. EVALUATIONS AT END OF TREATMENT

The EOT visit will be scheduled at 30 days after the last dose of study treatment (a window of \pm 7 days is allowed), unless the patient starts a new antitumor therapy or dies within those 30 days from the last dose, in which case the date of administration of this new antitumor therapy or the date of death will be considered as EOT.

For treated patients, regardless of the reason for discontinuation, if no recent data are available (i.e., within last 10 days prior to the EOT visit) or if the last data available show a grade ≥ 2 alteration, the following work-up will have to be done at this EOT visit:

- Complete physical examination, including weight (height only at baseline).
- ECOG performance status.
- Vital signs (heart rate, blood pressure, body temperature).
- Coagulation panel.
- Hematology.
- Biochemistry A.
- Biochemistry B.
- Pregnancy test, if clinically indicated.
- Electrocardiogram (ECG), if clinically indicated.
- LVEF by echocardiography (ECHO) or MUGA, if clinically indicated.
- Radiological and/or clinical tumor assessment (if not previously done and if the reason for treatment discontinuation was other than PD).
- Intercurrent events, concomitant diseases and treatments.
- Safety assessment (AEs).

Adverse events (AEs) and serious adverse events (SAEs) must be reported until 30 days after the last PM01183 administration (for safety reporting see Section [11.2](#)).

The Sponsors will evaluate all safety information that is spontaneously reported by an Investigator beyond the time frame specified in the protocol.

Patients of childbearing potential who use adequate contraception methods while on study should be reminded to continue adequate contraception for a period of six weeks after last study drug administration.

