11.2. PROCEDURES

11.2.1. Reporting Adverse Events

The Sponsors will collect AEs until 30 days after administration of the last dose of study drug, until the start of new antitumor therapy, or until the date of death, whichever occurs first. All AEs suspected to be related to the study drug must be followed-up after the time of therapy discontinuation until the event or its sequelae resolve to grade ≤ 1 or stabilize at an acceptable level to the Investigator and the Sponsors.

All AEs must be recorded in English using medical terminology in the source document and the CRF. Whenever possible, the Investigator will record the main diagnosis instead of the signs and symptoms normally included in the diagnoses.

Investigators must assess severity (grade) of the event following the NCI-CTCAE, version 4, and assign a relationship to each study drug; and pursue and obtain information adequate both to determine the outcome and to assess whether it meets the criteria for classification as a SAE requiring immediate notification to Pharma Mar S.A. or its designated representative. The Investigator must provide any relevant information as requested by the Sponsors in addition to that on the CRF.

Abnormal laboratory tests occurring during the study should only be recorded in the AE section of the CRF if the disorder:

- Is associated with clinically significant symptoms, and/or
- Represents a reason for change in study dosing or for discontinuation from the study treatment, significant additional concomitant drug treatment or other therapy, and/or
- Leads to any of the outcomes included in the definition of a SAE.

Otherwise, laboratory results should be reported in the corresponding section of the CRF (e.g., biochemistry, hematology).

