#### ***8.4 Treatment Administration***

Total cumulative dose, dose intensity and relative dose intensity, time on treatment, cycle delays and dose reductions will be described following standard tables detailed in Appendix I.

Total cumulative dose, expressed in mg, is the sum of all the study drug doses from the first cycle until last cycle, including the dose received in last cycle.

Patients will be considered to be on-treatment for the duration of their treatment and 30 days following the last treatment dose. If the patient starts any new antitumor therapy outside this clinical trial or dies within 30 days of last treatment dose, the date of administration of this new therapy or the date of death will be considered the date of treatment discontinuation.

However, as a convention, the duration of the last cycle is considered to be 21 days (instead of 30 days) for dose intensity calculation purposes.

Intended dose intensity (mg/m^2) is the planned dose per cycle divided by the planned number of weeks per cycle.

Absolute dose intensity (mg) is the actual cumulative dose divided by the number of weeks of treatment. Relative dose intensity (%) is the ratio of absolute dose intensity divided by the intended dose intensity.

The item of the case report form (CRF) «Infusion delayed: yes/no» will be used to calculate the delayed cycles. For those cycles considered as delayed by the investigator, the delay will be calculated as:

Delay: Date of current drug administration – Date of previous drug administration – 21.

The infusion of the first cycle will be excluded from all calculations regarding cycle delays and modifications.

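### A dose can be held until day 42 after the last infusion, but end of treatment and routine AE collection are set at day 30 (day 37 in one table), so some late findings count only if the patient is dosed again

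*Protocol*

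**What the plan says.** **The hold.** Protocol 5.2.1 sets the cycle ("three weeks = one treatment cycle"). Under 5.2.2, a patient who does not meet the criteria on the due date is re-tested ("re-assessments will be performed every 48-72 hours"), and the dose waits: "Treatment will be then withheld, up to a maximum of three weeks beyond its due date, until appropriate recovery". If she has still not recovered, she "must be withdrawn from the trial, except in case of objective clinical benefit", with Sponsors' agreement needed for the exception. Section 6.2.1.2 lists a delay of more than three weeks past the due date among the reasons for ending treatment.

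**The safety window.** All of these limits count from the last dose actually given:
- Protocol 6.2.1.1, EOT date: "By convention, the date of end of treatment will be 30 days after the date of last administration of study drug". It is earlier if new antitumor therapy or death comes first.
- Protocol 6.7, EOT visit: "The EOT visit will be scheduled at 30 days after the last dose of study treatment", with a tolerance of 7 days either side.
- Protocol 11.2.1, AEs: "The Sponsors will collect AEs until 30 days after administration of the last dose of study drug". Section 11.2.2 uses the same 30 days for SAEs, after which only those suspected to be related are collected.
- Protocol 6.6, Table 5: AEs through 30 ± 7 days after the last administration.
- SAP 8.4: "Patients will be considered to be on-treatment for the duration of their treatment and 30 days following the last treatment dose".

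Neither document says what applies to a patient who is still on hold after day 30.

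**The concern.** Two clocks run from the same infusion and do not agree. The stopping reason in 6.2.1.2 (delay over three weeks) cannot arise until day 42 has passed, yet by then the EOT date is at least 12 days old and the EOT visit window has closed. Between days 31 and 42 the patient is under two regimes at once: re-testing every 48-72 hours as a re-treatment candidate (5.2.2), and post-EOT follow-up of related AEs every four weeks (6.2).

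The statistical consequence is an outcome-dependent cut-off. Take two patients with the same new event on day 35. If one recovers and is dosed on day 42, the event lies inside continuous collection. If the other is withdrawn, it lies beyond day 30. Whether it is counted depends on later recovery, which is itself linked to toxicity. SAP Tables 12.2.2.4 and 12.2.2.5 present AEs regardless of relationship, and SAP 7.2 summarises worst laboratory grades during treatment, so the rule reaches planned outputs.

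**Working it through.** The 30-day window is a stated convention, so there is no formula behind it to reproduce. The check is day arithmetic, with day 0 as the last infusion given.

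**Inputs**
- Cycle length: 21 days (Protocol 5.2.1).
- Maximum hold: 21 days past the due date (5.2.2).
- EOT date and end of routine AE/SAE collection: day 30 (6.2.1.1, 11.2.1, 11.2.2; the SAP 8.4 on-treatment period agrees).
- Alternative end of AE collection: day 30 + 7 = 37 (Table 5).
- EOT visit window: days 30 − 7 = 23 to 30 + 7 = 37 (6.7).

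**Latest permitted re-dose**
- 21 + 21 = day 42.
- Cross-check with the delay formula in SAP 8.4 (current date − previous date − 21): 42 − 0 − 21 = 21 days, which matches the three-week maximum.

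**Which holds are affected**
- With a day-30 end: holds longer than 30 − 21 = 9 days.
- With a day-37 end: holds longer than 37 − 21 = 16 days.

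**Size of the gap for a patient held to the limit and not re-dosed**

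| End of collection | Days not covered | Gap | Share of the 42 days | Hold days covered |
|---|---|---|---|---|
| Day 30 (11.2.1, SAP 8.4) | 31-42 | 42 − 30 = 12 | 12/42 = 28.6% | 9 of 21 |
| Day 37 (Table 5) | 38-42 | 42 − 37 = 5 | 5/42 = 11.9% | 16 of 21 |

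The latest ordinary stop decision falls 12 days after the EOT date and 5 days after the EOT visit window closes. Where a longer hold is agreed, these figures grow.

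**The same days for a patient who is re-dosed.** Dosing on day 42 restarts the clock, so collection runs without a break to day 42 + 30 = 72. Days 31-42 are fully covered.

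**What falls in the gap and what does not, if she is not re-dosed**
- Not routinely collected: non-serious AEs, related or not, with onset in the gap (11.2.1), and SAEs in the gap that are not suspected to be related (11.2.2).
- Measured but outside the on-treatment period: laboratory grades from the 48-72-hour tests, if the SAP 8.4 definition governs the during-treatment summaries in SAP 7.2.
- Still captured: the abnormality that caused the hold, since it is present at the Day 1 check around day 21. If related, it is followed to grade ≤ 1 or stabilization (6.2, 6.8, 11.2.1).
- Still captured: related SAEs, with no end date (11.2.2), and deaths by cause with time from last dose, with no 30-day limit (SAP Table 12.3.2.1 and Listing 12.3.2.2).

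**The case against.** The strongest reply is that last dose plus 30 days is a deliberate convention, applied identically to every patient. Re-dosed patients count days 31-42 because they are still on treatment, which any rule of this kind produces. That is fair, and it disposes of one inference a reader might draw: that patients with prolonged toxicity get the shortest safety window. The post-dose window has the same length for everyone, and only new antitumor therapy or death shortens it.

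A reader might also infer that events in patients who never recover are dropped, or that SAEs and unrelated deaths are understated across the board. The documents do not support this. The triggering toxicity, related SAEs and deaths each have a reporting route after day 30, and spontaneous late reports are evaluated (6.7, 11.2.2). An unrelated fatal event on day 38 could miss SAE reporting, but the death and its cause would still be tabulated.

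Quoting 29% alone would also mislead, because Table 5 supports a gap of 5 days. Worst grades change only if a new maximum occurs after day 30. In the phase I data (Protocol 1.2.1.2; 15 patients at the recommended dose), the neutropenia nadir generally came around Day 13, and neutropenia lasted a median of three days and caused no delays at that dose. SAP 8.4 is an exposure section, and SAP 7.1.1 does not itself cut AE tables at day 30.

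What survives is narrower. EOT can precede the decision that ends treatment, Table 5 disagrees with 11.2.1, and three categories of late finding depend on re-dosing.

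**Conclusion.** The point holds in limited form. For patients stopped after a hold of more than 9 days and not re-dosed, EOT can precede the stop decision. It must do so whenever the reason is a delay of more than three weeks. New-onset non-serious AEs, SAEs not suspected to be related, and laboratory grades in a gap of 5 to 12 days count only if the patient is later dosed again.

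The lower figure assumes Table 5 sets the end of AE collection, and the upper assumes 11.2.1 and SAP 8.4 do. Both assume a hold that runs to the three-week limit; shorter holds leave a smaller gap. The laboratory part also assumes that SAP 8.4 defines during treatment for the worst-grade tables.

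The documents give no rate of holds beyond 9 days, so the number of patients cannot be computed. It is probably small, and nothing here shows a material bias in the overall safety profile. In a group of 20, the planned size of Cohort A1, one missed patient would move an incidence by 1/20 = 5 percentage points. This is an inexpensive clarification worth making.

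**What to change.** - In Protocol 11.2.1, 11.2.2 and Table 5, and in SAP 8.4, end AE and laboratory reporting at the later of 30 days after the last dose and the recorded date of the decision to discontinue. New antitumor therapy or death still cuts the period. Protocol 6.7 and 7.2 repeat the 30-day limit and need matching wording.
- Keep the 30-day convention for time on treatment.
- Reconcile the EOT date (6.2.1.1), the EOT visit window (6.7) and the ± 7 days in Table 5 with the hold in 5.2.2 and the stopping reason in 6.2.1.2. Say explicitly which rules apply to a patient still on hold after day 30. The permitted hold itself is not in question and need not change.
- Make sure the date of the discontinuation decision is recorded. Section 6.2.1.1 asks for the reason but does not mention that date.

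**Cost.** Wording in both documents, possibly one CRF date, and up to about 12 more days of AE recording in a few patients who are already being re-tested every 48-72 hours (longer where an extended hold is agreed). AE counts may rise slightly. The real trade-off is that the post-dose window will no longer be the same length for every patient, which the safety tables should state in a footnote.
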